7.4.1.3 Cumulative Dose, Dose Intensity, and Relative Dose Intensity

A subject’s cumulative dose of lenalidomide is defined as the sum of each dose they took, as recorded in their medication diary. In order to compute the cumulative dose of dexamethasone, IV dexamethasone will have to be converted to its equivalent oral dose. This will be done by treating each mg of IV dexamethasone as 1.32 mg of oral dexamethasone, i.e. making use of the fact that the mean bioavailability of oral dexamethasone was estimated to be 0.76. A subject’s cumulative dose of dexamethasone will be defined as the sum of all dexamethasone doses, oral and IV, converted to oral equivalent. The cumulative dose administered will be summarized for each of these drugs, by treatment group.

Elotuzumab:

A subject’s cumulative dose of elotuzumab is measured in mg/kg, and is defined as the sum of their elotuzumab doses (mg/kg) (actual, not planned) over all infusions.

Elotuzumab dose intensity (mg/kg/week) and relative dose intensity per subject will be calculated separately for Cycles 1 and 2, and Cycles 3 and beyond cycle 18, since elotuzumab planned dose intensity in Cycles 1 and 2 differs from that in Cycles 3 and beyond.

Cycle 1 and 2

$$7 \times \left(\frac{\text{cumulative dose of elotuzumab during the first 2 cycles}}{\left(\frac{\min(\text{date of first dose of elotuzumab in the last cycle among the first 2 cycles} + 28, \text{death date}) - \text{date of first dose of elotuzumab in Cycle 1}}{\text{date of first dose of elotuzumab in Cycle 1}} \right)} \right)$$

Cycle 3 and beyond

$$7 \times \left(\frac{\text{cumulative dose of elotuzumab starting from Cycle 3}}{\left(\frac{\min(\text{date of first dose of elotuzumab in last cycle} + 28, \text{death date}) - \text{date of first dose of elotuzumab in Cycle 3}}{\text{date of first dose of elotuzumab in Cycle 3}} \right)} \right)$$

The relative dose intensity will be calculated as

$$\text{Dose Intensity/Planned Dose Intensity(PDI)}$$

Planned dose per week for elotuzumab is 10mg/kg/week for the first 2 cycles, 5mg/kg/week for cycles 3 and beyond. The PDI per subject for elotuzumab will be computed by averaging the planned doses per week over the treatment duration e.g., elotuzumab PDI for a subject whose last dose was the first dose of third cycle would have the PDI computed as

$$\text{Elotuzumab PDI ((mg/kg/wk)} = \frac{4 \times 10 + 4 \times 10 + 4 \times 5}{12}$$

Dose intensity and relative dose intensity of elotuzumab will be summarized for the E-Ld group only.

Lenalidomide:

A subject’s cumulative dose of lenalidomide is defined as the sum of each dose taken, as recorded in their medication diary.

Dose intensity and relative dose intensity for lenalidomide (mg/week) will be calculated separately for subjects who began the study at the standard daily dose, 25mg/day and those who, because of moderate renal impairment, began the study at < 25mg/day (at 10mg/day dose will be assumed when computing the RDI as this is the recommended dose for subject with moderate renal disease per protocol).

The lenalidomide dose intensity, per subject, will be calculated as:

$$7 \times \left(\frac{\left(\frac{\text{cumulative dose of lenalidomide}}{\left(\frac{\min(\text{date of 1st dose of lenalidomide in last cycle in which lenalidomide was administered} + 28, \text{death date}) - \text{date of first dose of lenalidomide}}{\text{date of first dose of lenalidomide}} \right)} \right)}{\left(\frac{\text{cumulative dose of lenalidomide}}{\left(\frac{\text{start date of last cycle in which lenalidomide was administered} - \text{date of first dose of lenalidomide} + 28}{\text{date of first dose of lenalidomide}} \right)} \right)} \right)$$

The relative dose intensity of lenalidomide is the dose intensity per week divided by the planned dose intensity per week, 131.25mg (or 52.5mg for subjects who begin therapy at <25mg/day(10mg/day per protocol)).

Dexamethasone:

The dose intensity (mg/week) of dexamethasone, per subject, will be calculated separately for the period encompassing Cycles 1 and 2, Cycle 3-18 and Cycle 19 and beyond since dexamethasone dosing is different in these 3 periods.

Cycle 1 and 2:

$$7 \times \left(\frac{\text{cumulative dose of dexamethasone during the first two cycles}}{\left(\min(\text{date of first dose of dexamethasone in last cycle among first 2 cycles} + 28, \text{death date}) - \right) \text{date of first dose of dexamethasone in first cycle}} \right)$$

Cycle 3-18:

$$7 \times \left(\frac{\text{cumulative dose of dexamethasone during Cycle 3 – Cycle 18}}{\left(\min(\text{date of first dose of dexamethasone in last cycle among 18 cycles} + 28, \text{death date}) - \right) \text{date of first dose of dexamethasone in Cycle 3}} \right)$$

Cycle 19 and beyond:

$$7 \times \left(\frac{\text{cumulative dose of dexamethasone starting from Cycle 19}}{\left(\min(\text{date of first dose of dexamethasone in last cycle} + 28, \text{death date}) - \right) \text{date of first dose of dexamethasone in Cycle 19}} \right)$$

The relative dose intensity of dexamethasone is the dose intensity per week divided by the planned dose intensity per week. The planned dose of dexamethasone in the experimental arm on elotuzumab dosing days, 8mg IV dexamethasone plus 28mg oral dexamethasone, is equivalent to 38.5mg of oral dexamethasone. The planned dose in the experimental arm when dexamethasone is not being administered with elotuzumab is 40mg. Thus, the planned weekly dose of dexamethasone in the experimental arm for Cycles 1 and 2 will be equivalent to 38.5mg oral dexamethasone, the planned weekly dose of dexamethasone in the experimental arm for Cycle 3 - Cycle 18, during which IV dexamethasone is given on Days 1 and 15 only, will be equivalent to 39.25mg of oral dexamethasone and the planned weekly dose of dexamethasone in the experimental arm for Cycle 19 and beyond, during which IV dexamethasone is given on Days 1 only, will be equivalent to 39.64mg of oral dexamethasone. The planned weekly dose of dexamethasone in the control arm is 40mg for all cycles.

In the dose intensity formulas, if the patient took a dose on his death date then 1 day will be added to the denominator.

Descriptive statistics (n, mean, STD, median, min, max, q1 and q3) will be presented for the cumulative dose, and dose intensity of each agent, by treatment group. The number and percentage of subjects whose relative dose intensity falls into the following categories will be presented, by treatment group: $\geq 90\%$, 80% to $< 90\%$, 70% to $< 80\%$, 60% to $< 70\%$, $< 60\%$.

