4.5 Selection and Timing of Dose for Each Subject

4.5.1 Study Drug Administration

Dexamethasone

On weeks without elotuzumab (including the control arm), administer the weekly dose of 40 mg dexamethasone on Day 1, 8, 15, and 22 (-1 to +3 days). At the investigator's discretion, the oral dexamethasone may be given as a split dose over 2 consecutive days each week.

On weeks of elotuzumab infusion, administer dexamethasone as a split dose of:

- 28 mg po (between 3 - 24 hours prior to the start of elotuzumab infusion) AND
- 8 mg IV (on the day of elotuzumab infusion at least 45 min prior to the start of infusion).
- At the discretion of the investigator, the oral dexamethasone component may be given as a split dose 12 - 24 and 3 hours prior to elotuzumab.

Elotuzumab

Elotuzumab will be administered intravenously at a dose of 10 mg/kg weekly (Days 1, 8, 15, and 22 of a 4-week cycle) of the first 2 cycles and every 2 weeks (Day 1 and Day 15) for Cycles 3 through 18, then at a dose of 20 mg/kg every 4 weeks Cycle 19 (Day 1) and beyond. A window of -1 to +3 days is permitted in Cycles 1 and 2.

In Cycle 1 and 2, an elotuzumab dose that falls outside of the pre-specified window must be skipped.

In Cycles 3 and beyond, elotuzumab dosing may be delayed for up to 1 week as clinically indicated. The reason for the delay must be recorded on the CRF. If unable to administer within 1 week, then the dose should be skipped and resumption of the elotuzumab continues per the protocol defined schedule.

In addition, the following must also be administered 30 - 90 min prior to any elotuzumab:

- H1 blocker: diphenhydramine (25 - 50 mg po or IV) or equivalent
- H2 blocker: ranitidine (50 mg IV) or equivalent
- Acetaminophen (300 - 1000 mg po).

See [Appendix 3](#) for elotuzumab dosing instructions.

Lenalidomide

Lenalidomide will be taken orally 25 mg once daily for the first 3 weeks of a 4-week cycle. On the days of elotuzumab administration, the dose of lenalidomide is to be administered at least 2 hours after completion of elotuzumab dosing. Subjects should not break, chew or open the capsules.

Table 4.5.1-1: Treatment Schedule

Investigational Arm (ELd Arm)												
Cycle #	1 - 2				3 - 18				19 +			
Day # (-1/+3 days)^a	1	8	15	22	1	8	15	22	1	8	15	22
Dexamethasone - PO	28 mg	28 mg	28 mg	28 mg	28 mg	40 mg	28 mg	40 mg	28mg	40 mg	40 mg	40 mg
Dexamethasone - IV	8 mg	8 mg	8 mg	8 mg	8 mg	-	8 mg	-	8 mg	-	-	-

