4.5.3 Dose Delay or Interruption

If the dose of one drug in the regimen (ie, lenalidomide, dexamethasone or elotuzumab) is delayed or interrupted, the treatment with the other drugs may continue as scheduled. Subjects experiencing a 28-day delay in all study drugs lenalidomide, dexamethasone, and elotuzumab due to an adverse event(s) related to study treatment must be discontinued from study drug. Subjects experiencing delays unrelated to study therapy, for example due to radiation therapy may delay study treatment up to 42 days. Delays greater than 28 days must be discussed with the medical monitor.

Each cycle is 28 days. While dose delays or interruptions are permitted, the start of each cycle cannot be delayed and is fixed relative to Cycle 1 Day 1. Adjustments to the Cycle 1 Day 1 anchored schedule should not be performed. Missed doses should be skipped, not delayed, if not given within the allowed window.

Subjects may continue on study therapy even if components of the study therapy must be discontinued. For example, a subject on lenalidomide and dexamethasone may continue on study therapy even if dexamethasone must be discontinued for an adverse event. Likewise, a subject on

the investigational arm may continue on study therapy if elotuzumab must be discontinued for an adverse event or other reason. Patients are considered still on study therapy even if they continue solely on lenalidomide.

Please consult the BMS medical monitor or any questions regarding dose interruption or study therapy discontinuation.

4.5.3.1 *Elotuzumab*

In Cycle 1 and 2, an elotuzumab dose that falls outside of the pre-specified window (-1 to +3 days) must be skipped.

In Cycles 3 and beyond, elotuzumab dosing may be delayed for up to 1 week. If unable to administer within 1 week, then the dose should be skipped and resumption of the elotuzumab continues per the protocol defined schedule.

4.5.3.2 *Dexamethasone*

Dexamethasone delay should be performed as clinically indicated at the discretion of the investigator.

For subjects receiving elotuzumab, the weekly dexamethasone dose that coincides with or is temporally closest to the elotuzumab dosing must be administered as part of the premedication for elotuzumab per the guidance in [Section 4.5.1](#).

4.5.3.3 *Lenalidomide*

Lenalidomide delay should be performed as clinically indicated at the discretion of the investigator.

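### Dose-intensity windows follow the doses given rather than the fixed cycle calendar, so over short exposure the same delivered elotuzumab dose can score 100%, 87.5% or 77.8%

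*SAP*

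**What the plan says.** SAP 7.4.1.3 defines dose intensity as 7 times the cumulative dose divided by a number of days, and RDI as that figure divided by a planned weekly intensity. Elotuzumab is handled separately for Cycles 1-2 and for Cycle 3 onward. In the later period the window opens at the "date of first dose of elotuzumab in Cycle 3" and closes 28 days after the "date of first dose of elotuzumab in last cycle", or at death if that comes first. The Cycles 1-2 formula and the three dexamethasone formulas have the same shape. The only adjustment printed is one extra day when a dose was taken on the date of death.

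For lenalidomide two expressions appear. One has the same shape; the other closes the window from the "start date of last cycle in which lenalidomide was administered". Results are tabulated by arm as the number of subjects "whose relative dose intensity falls into the following categories": at least 90%, then three 10-point bands, then below 60%.

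The protocol runs on a fixed calendar. Section 4.5.3 states that "the start of each cycle cannot be delayed and is fixed relative to Cycle 1 Day 1" and that "Missed doses should be skipped, not delayed, if not given within the allowed window". Section 4.5.1 sets elotuzumab at "10 mg/kg weekly (Days 1, 8, 15, and 22 of a 4-week cycle) of the first 2 cycles" and, for those cycles, says that "an elotuzumab dose that falls outside of the pre-specified window must be skipped". From Cycle 3 an elotuzumab dose may be given up to one week late.

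**The concern.** On a fixed calendar, the time over which drug was due does not depend on when drug was given. The SAP window does depend on it, at both ends.

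- If the first dose of the period is skipped or late, the window opens late. The lost time disappears from the denominator and the miss is forgiven.
- If the first dose of the last cycle is skipped or late, the window closes after that cycle has ended. The miss is counted in the numerator and again in the denominator.
- If no elotuzumab is given in Cycle 3 but it is resumed later, the start date does not exist, and no fallback is given.

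Planned intensity is a fixed weekly figure, so any error in the window passes straight into RDI and can change a subject's reporting band. With 40 subjects per arm, each subject placed in the wrong band moves that band by 1/40 = 2.5 percentage points. Short exposures are the most distorted, and these include subjects who stop early.

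**Working it through.** **Inputs.** 28-day cycles fixed to Cycle 1 Day 1 (Protocol 4.5.3). Elotuzumab 10 mg/kg on Days 1, 8, 15 and 22 in Cycles 1-2, and on Days 1 and 15 in Cycles 3-18 (Protocol 4.5.1). Planned intensity 10 and then 5 mg/kg/week (SAP 7.4.1.3).

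**Formula.** RDI = [7 × cumulative dose / (first dose in last cycle + 28 − first dose given)] / planned intensity.

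**Reproducing the plan.** Planned intensity is 4 × 10/4 = 10 in Cycles 1-2, 2 × 10/4 = 5 in Cycles 3-18 and 20/4 = 5 from Cycle 19, as the SAP states. With every dose on schedule in Cycles 1-2, the window is 29 + 28 − 1 = 56 days and RDI = 7 × 80/56/10 = 100%. The formula is right when nothing is missed or moved.

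**One of eight doses skipped (70 mg/kg delivered, true value 7/8 = 87.5%).**

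| Dose skipped | Cycles 1-2 window | Cycles 3-6 window | RDI, both periods |
|---|---|---|---|
| First of the period | (29+28)−8 = 49 days | 98 days | 100% |
| Any of the other six | 56 days | 112 days | 87.5% |
| Day 1 of the last cycle | (36+28)−1 = 63 days | 126 days | 77.8% |

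Check for Cycles 3-6: 7 × 70/98 = 5.00, 7 × 70/112 = 4.375 and 7 × 70/126 = 3.89 mg/kg/week, each divided by 5. The three results fall in three reporting bands.

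**No dose lost, permitted 7-day delay, Cycles 3-4 (40 mg/kg delivered, true value 100%).** Counting Cycle 3 Day 1 as day 1:
- Cycle 3 Day 1 delayed: (29+28)−8 = 49 days; 7 × 40/49/5 = 114.3%.
- Cycle 4 Day 1 delayed: (36+28)−1 = 63 days; 7 × 40/63/5 = 88.9%.

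**Dexamethasone, control arm, 40 mg weekly, Cycles 1-2.** Skipping the first dose, the Day 8 dose of Cycle 1, or Cycle 2 Day 1 gives 100%, 87.5% and 77.8%, by the same arithmetic.

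**Lenalidomide, two cycles, first 7 days of Cycle 2 missed (35 of 42 doses, true value 83.3%).** The expression ending from the first dose gives 7 × 875/63/131.25 = 74.1%. The one ending from the cycle start gives 7 × 875/56/131.25 = 83.3%. If instead the first 7 days of Cycle 1 are missed, both give 7 × 875/49/131.25 = 95.2%, because both open at the first dose given.

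**How the effect fades.** Take m cycles from Cycle 3 (m from 2 to 16), with 2m doses planned and one skipped. The window is 28m days, shortened or lengthened by 14. The three results are 100%, (2m−1)/2m and (2m−1)/(2m+1).

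| Last cycle | First skipped | Other dose skipped | Last-cycle Day 1 skipped | Bands |
|---|---|---|---|---|
| 4 | 100% | 75% | 60% | three |
| 6 | 100% | 87.5% | 77.8% | three |
| 7 | 100% | 90% | 81.8% | two |
| 12 | 100% | 95% | 90.5% | one |
| 18 | 100% | 96.9% | 93.9% | one |

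**Data cut-off.** The window is cut short only by death, so an unfinished last cycle is charged 28 days. The analysis takes place at least 6 months after the last subject's first treatment (SAP, Schedule of Analyses). At 30.4375 days per month (SAP 8.4) that is 182.6 days, so the last subject is at about Cycle 7 Day 15 or later. A fully dosed lenalidomide subject there scores (126+15)/147 = 95.9%. Below 90% are only Cycle 8 Days 1-4 (lowest 148/168 = 88.1%) and Cycle 9 Days 1-2 (lowest 169/189 = 89.4%). From Cycle 10 the lowest value is 190/210 = 90.5%.

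**The case against.** The strongest reply is that the effect is narrow and the tables are descriptive. Much of that stands.

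- In the eight-dose example, six of the eight possible skips give the right answer. The 100% result in Cycles 1-2 needs elotuzumab missed on Cycle 1 Day 1 while the other drugs start; the protocol allows this, but it is probably uncommon.
- Subjects still on elotuzumab at the planned analysis have reached at least Cycle 7. The three-band spread in the Cycle 3+ window therefore concerns those who stopped elotuzumab by Cycle 6. The Cycles 1-2 window, however, is short for everyone and does not improve with follow-up.
- The paired lenalidomide expressions may be an artefact of reading an equation from PDF, so little should rest on them.

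A reader might infer more than the documents support:

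- **Cut-off.** One might take a fully dosed subject cut off on Cycle 7 Day 1, at 127/147 = 86.4% for lenalidomide, as typical. At the planned analysis the last subject is already about two weeks past that day, and the other subjects still on treatment are later. Only the few days in Cycles 8 and 9 shown above remain.
- **Deliverability.** One might conclude that the trial cannot show whether the regimen was deliverable. SAP 7.4.1.1 and 7.4.1.2 also report cycles received, subjects on each drug by cycle, and delays, omissions, reductions and interruptions, with reasons for most of them.
- **Comparison and efficacy.** The same rules apply to both arms for lenalidomide and dexamethasone, and no bias between arms is shown. Nothing here touches the response-rate test.

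**Conclusion.** Wrong as written, and worth correcting. The SAP window contradicts the protocol's fixed calendar, and the error follows directly from the printed formula. It arises only when the skipped or delayed dose is the first of the period or the first of the last cycle. For 7 of 8 elotuzumab doses it shifts RDI from 87.5% to 100% or 77.8%. For a permitted one-week delay over Cycles 3-4 it shifts RDI from 100% to 114.3% or 88.9%. In the Cycle 3+ window one skipped dose spans three bands when the last cycle is 4, 5 or 6, and stays in the top band by Cycle 12. The missing start date when no elotuzumab is given in Cycle 3 is a separate gap.

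The figures assume doses on their planned days apart from the one skipped or delayed, full 10 mg/kg doses, no death in the window, and cycles anchored as in Protocol 4.5.3. How many subjects would change band cannot be known from the documents. The consequence is confined to descriptive exposure tables.

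**What to change.** Use one rule for elotuzumab, lenalidomide and dexamethasone.

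1. Open each period at its planned Day 1: for cycle k, Cycle 1 Day 1 + 28 × (k−1).
2. Close it at the earliest of the planned end of the last cycle in which the drug was given, death, and data cut-off.
3. Compute RDI as dose delivered divided by dose scheduled within that window. This replaces division by a fixed weekly figure, and it also handles a partly elapsed last cycle.
4. Keep a single lenalidomide expression that agrees with this rule.

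Under this rule 7 of 8 doses gives 87.5% whichever one is skipped, a permitted delay with all doses given returns 100%, and a subject with no elotuzumab in Cycle 3 has a defined start.

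The cost is SAP wording and programming on dates already collected. Some subjects move to a lower band (100% to 87.5%) and some to a higher one (77.8% to 87.5%). Cycles after the last one dosed stay uncounted, as now. Position therefore still matters there: losing both doses of Cycle 6 gives 6/6 = 100%, while losing both of Cycle 4 gives 6/8 = 75%. That is an acceptable convention if a table footnote states it.

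### Elotuzumab relative dose intensity divides a period-specific dose intensity by a planned intensity averaged over the whole treatment, so full dosing does not score 100% in subjects who reach Cycle 3

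*SAP*

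**What the plan says.** All of this is in SAP 7.4.1.3.

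- **Periods.** Elotuzumab dose intensity and "relative dose intensity per subject will be calculated separately for Cycles 1 and 2, and Cycles 3 and beyond cycle 18". The stated reason is that planned intensity differs between the two periods.
- **Numerators.** There are two dose-intensity formulas. One uses the "cumulative dose of elotuzumab during the first 2 cycles", the other the "cumulative dose of elotuzumab starting from Cycle 3", each over the days of its own period. There is no formula for the whole treatment.
- **Planned rates.** "Planned dose per week for elotuzumab is 10mg/kg/week for the first 2 cycles, 5mg/kg/week for cycles 3 and beyond".
- **Denominator.** RDI is dose intensity divided by planned dose intensity (PDI), and "The PDI per subject for elotuzumab will be computed by averaging the planned doses per week over the treatment duration". The example, "for a subject whose last dose was the first dose of third cycle would have the PDI computed as" shown, is (4×10 + 4×10 + 4×5)/12.
- **Reporting.** "The number and percentage of subjects whose relative dose intensity falls into the following categories will be presented": ≥90%, 80 to <90%, 70 to <80%, 60 to <70% and <60%. Elotuzumab RDI is summarized for the ELd arm only.

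Dexamethasone, in the same section, is handled differently. Each of its three periods has its own dose intensity and its own planned weekly dose (38.5, 39.25 and 39.64 mg in the ELd arm).

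**The concern.** A relative dose intensity should be 100% when a subject receives exactly what was planned. That requires numerator and denominator to cover the same time. Here the numerator covers one period and the denominator mixes two periods whose planned rates differ by a factor of two. Cycles 1-2 are compared with a plan that is too low, and Cycle 3 onward with a plan that is too high. The size of the error changes with the number of cycles received.

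At stake is how the exposure table for the investigational drug is read. It could show missed elotuzumab from Cycle 3 where none was missed, and hide missed elotuzumab in Cycles 1-2.

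**Working it through.** **Inputs**
- Schedule (Protocol 4.5.1, SAP 6.2): 10 mg/kg four times per cycle in Cycles 1-2, 10 mg/kg twice per cycle in Cycles 3-18, and 20 mg/kg once per cycle from Cycle 19.
- Planned weekly rate: 40/4 = 10 mg/kg in Cycles 1-2; 20/4 = 5 mg/kg from Cycle 3. The Cycle 19 change leaves the weekly rate at 5.
- Cycles are taken as exactly 28 days, with every dose given on its scheduled day.

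**Step 1: the SAP's own example.** (40 + 40 + 20)/12 = 100/12 = 8.33 mg/kg/week. It counts all four weeks of Cycle 3 and pools both periods.

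**Step 2: general PDI.** For N ≥ 2 cycles:

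PDI = [2×4×10 + (N−2)×4×5]/(4N) = (40 + 20N)/(4N) = 5 + 10/N.

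At N = 3 this gives 8.33, matching the example.

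**Step 3: dose intensity under perfect dosing, by the SAP formulas.**
- Cycles 1-2: 7 × 80/56 = 10 mg/kg/week.
- Cycle 3 onward: 7 × 20/28 = 5 mg/kg/week, whatever the number of cycles.

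**Step 4: RDI as written.**
- Cycles 1-2: 10/(5 + 10/N) = 2N/(N+2).
- Cycle 3 onward: 5/(5 + 10/N) = N/(N+2).

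| Cycles N | PDI (mg/kg/week) | RDI, Cycles 1-2 | RDI, Cycle 3 onward | Category, Cycle 3 onward |
|---|---|---|---|---|
| 3 | 8.33 | 120% | 60% | 60 to <70% |
| 6 | 6.67 | 150% | 75% | 70 to <80% |
| 12 | 5.83 | 171% | 86% | 80 to <90% |
| 18 | 5.56 | 180% | 90% | ≥90% |
| 24 | 5.42 | 185% | 92% | ≥90% |
| limit | 5 | 200% | 100% | ≥90% |

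With period-specific PDIs of 10 and 5, both RDI columns are 100% in every row. A subject who stops in Cycle 1 or 2 has PDI = 10 and correctly scores 100%.

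**Step 5: where categories change from Cycle 3.** N/(N+2) ≥ 0.90 requires N ≥ 18, that is 18 × 28 = 504 days, or 504/30.4375 = 16.6 months. The SAP schedules the ORR analysis at least 6 months after the last subject's first treatment. Six months is 6 × 30.4375/28 = 6.5 cycles. A late-enrolled, fully dosed subject with six completed cycles at that point would be tabulated at 75%.

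**Step 6: masking in Cycles 1-2.** A subject given a fraction f of the planned dose in Cycles 1-2 scores f × 2N/(N+2). That reaches 90% when f ≥ 0.45(N+2)/N: 75% of plan at N = 3, 60% at N = 6, 50% at N = 18. Half the planned dose with 18 cycles therefore lands in the top category.

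**Step 7: the SAP's example subject.** With full dosing in Cycles 1-2 and one 10 mg/kg dose in Cycle 3, dose intensity from Cycle 3 is 7 × 10/28 = 2.5. As written, RDI is 2.5/8.33 = 30%; against the planned 5 it is 50%.

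**The case against.** The strongest defence is that the intent can be recovered. The SAP explains why it splits the periods, prints the planned 10 and 5, and uses period-matched plans for dexamethasone. The averaging sentence may be left over from an overall RDI. That is plausible, but the text gives an explicit instruction with an example that crosses periods, and it has no overall dose intensity for the average to serve. Nor can treatment duration sensibly mean duration within a period: the planned rate is constant in each, so there would be nothing to average.

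The second defence is that little depends on RDI, and this largely stands. The SAP also reports cycles and duration (7.4.1.1), delays, omissions and interruptions (7.4.1.2), and cumulative dose and dose intensity. The period-specific dose intensity is correct and can be compared directly with 10 and 5. RDI enters no efficacy analysis or decision rule described in the SAP, and it can be recomputed from the dosing data.

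A reader might infer more than the documents support:
- *That Cycles 1-2 are inflated for everyone.* Only subjects who reach Cycle 3 are affected.
- *That RDI no longer reflects dose received.* The numerator is the actual dose, so RDI depends on both delivery and time on treatment.
- *That every fully dosed subject falls into a low category from Cycle 3.* This holds only below 18 cycles.
- *That values such as 120% or 185% misclassify the subjects concerned.* The top category is open, so a fully dosed subject at 185% shares a cell with one at 100%. The harm in Cycles 1-2 is masked under-dosing.
- *That 185% is a ceiling.* It corresponds to about 24 cycles; the limit is 200%.

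**Conclusion.** Wrong as written. The period-specific dose intensities have no matching denominator, and the averaged PDI has no matching numerator. For subjects who reach Cycle 3, the RDI is multiplied by 2N/(N+2) in Cycles 1-2 and by N/(N+2) afterwards, relative to the value with a period-matched plan. In the reported categories this has two effects: false shortfall from Cycle 3 for fully dosed subjects with fewer than 18 cycles, and concealed shortfall in Cycles 1-2.

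The figures assume exact 28-day cycles and a PDI averaged over whole cycles, as in the SAP's example. The treatment lengths are illustrative. The documents give no expected distribution of cycles received, so the number of subjects misplaced cannot be derived.

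The consequence is confined to a descriptive exposure table for the ELd arm. The documents give no ground for extending it to ORR or PFS.

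**What to change.** For the period-specific RDI, delete the averaging sentence and its example. State that PDI is 10 mg/kg/week for Cycles 1-2 and 5 mg/kg/week for Cycle 3 onward, the SAP's own figures, paired by period as is already done for dexamethasone.

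If an overall RDI is also wanted, define an overall elotuzumab dose intensity (cumulative dose over all cycles divided by the time over all cycles) and use the averaged PDI only with that.

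The cost is SAP wording and a minor programming change. No new data are needed and no dosing rule is touched.
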